# Project summary

Study Title	The effect of interrupting sitting with regular active breaks on peripheral and cerebral blood flow in adults with type 1 diabetes			
Internal ref. no. / short title	Sitting and vascular health in people with T1D (ERN no: 2934)			
Proposed start date	01/02/2025			
Proposed end date	01/08/2026			
Countries in which the study will take place	England			
Study Design	Randomised crossover trial			
Study Participants	Habitually sedentary people type 1 diabetes using a closed-loop insulin delivery system			
Planned Sample Size	24			
Planned Study Period	18 months			
	Objectives	Outcome Measures		
Primary	To determine the effect of active breaks on change in superficial femoral artery flow-mediated dilation (FMD) compared to 7 hours compared to uninterrupted sitting.			
Secondary	To determine the effect active breaks compared to 7 hours of uninterrupted sitting on markers of glycaemia as assessed by continuous glucose monitoring (CGM). Glucose data gathered from closed-loop systems will be split into three time blocks; 1). 48 hours prior to the experimental period; 2). Experimental period (~7 hours); 3). 48 hours post-experimental period.	a) mean glucose b) % of time in level 2 hypoglycaemia (<3.0mmol/L) c) % of time in level 1 hypoglycaemia (3.0-3.9mmol/L) d) % of time in level 1 hyperglycaemia (10.0- 13.9mmol/L) e) % of time in level 2 hyperglycaemia (>13.9mmol/L) f) glycaemic variability, reported as CV and SD g) episodes of hypoglycaemia and hyperglycaemia h) area under the curve of episodes of hypoglycaemia and hyperglycaemia.		
	To determine the effect of active breaks on insulin dose compared to 7 hours compared to uninterrupted sitting.			

To determine the effect of active breaks on cerebrovascular function compared to 7 hours of uninterrupted sitting.	Middle cerebral artery velocity (MCAv)
To determine the effect of active breaks on markers of inflammation	
 
Endothelin-1 (ET-1) concentrations
 
Vascular cellular adhesion molecule concentrations (VCAM-1)
 

	
 
3) Intracellular adhesion molecule (ICAM-1)
 
4) Interleukin 6 (IL-6) concentrations
 

# Funding and support in kind

Funder(s)	Financial and non-financial support given
Na	Na

# Role of sponsor and funder

# Roles & responsibilities of management committees/groups & individuals

## Patient & public involvement group

Exercise for Type One Diabetes (EXTOD) PPI group

# Key words

activity breaks; glycemia; closed-loop; prolonged sitting; flow-mediated dilation

# Project flow chart

[figure not shown]

Figure 1. Study timeline schematic. PA, physical activity.

## **Protocol**

# 1. Background

The primary cause of mortality in people with T1D is cardiovascular disease (CVD) (Secrest et al., 2010). As such, individuals with T1D have a 3 times greater risk of developing CVD over their lifetime compared to the general population, with CVD events tending to occur earlier (Liese et al., 2013; Rawshani et al., 2017; Secrest et al., 2010). Diabetic vasculopathy often precedes overt symptoms of CVD such as atherosclerosis and is thought to be primarily driven by vascular dysfunction (Longendyke et al., 2023).

Sedentary behaviour has been identified as a risk factor for morbidity and mortality, independent of whether the general physical activity guidelines are being met (Biswas et al., 2015; Chau et al., 2013). Recent studies for individuals with T1D have examined the effect of breaking up prolonged periods of sedentary behaviour; individuals are encouraged to break up their sitting with brief, frequent bouts of standing and/or low-intensity physical activity (Alobaid et al., 2023; Campbell et al., 2023). Previous research on interrupting prolonged sitting has focused on healthy or prediabetic populations (Daniele et al., 2022) or on outcomes related to glucose regulation in T1D populations (Campbell et al., 2023). A recent study by Campbell et al. (2023) first demonstrated the potential of breaking up prolonged sitting to acutely improve glucose regulation in people with T1D. The study design incorporated 3-minute walking breaks (interrupting sitting) every half an hour during a 7-hour experimental window and found a 16% decrease in average glucose concentrations not only during the 7-hour experimental trial but also for 48 hours following the trial (Campbell et al., 2023). To date, the acute effects of breaking up sitting vascular function in T1D populations remain unexplored.

#### 2. Rationale

Therefore, this study will investigate the impact of breaking up 7 hours of sitting with 3-minute intervals of light-intensity walking every 30 minutes on vascular function in individuals with T1D. It is hypothesised that interrupting sitting will acutely improve vascular function and metrics relating to glucose management compared to prolonged sitting.

#### 3. Theoretical framework

To date, the acute effects of breaking up sitting on vascular function in T1D populations remain unexplored. We aim to advance the work of Campbell et al. (2023) by using the same protocol that has shown positive effects on glucose regulation to determine if there are positive effects on other domains of health.

#### 4. Research question/aims

We aim to investigate the influence of interrupting prolonged sitting with scheduled active breaks (3 mins of walking every 30 min) on peripheral and cerebral blood flow in adults with T1D using hybrid closed-loop insulin delivery systems. In addition, we aim to investigate markers of glycaemia, inflammation and total daily insulin dose.

#### 4.1. Objectives

#### 4.2. Outcome

	Objectives	Outcome Measures			
Primary	To determine the effect of active breaks on change in superficial femoral artery flow-mediated dilation (FMD) compared to 7 hours compared to uninterrupted sitting.	superficial femoral artery dilation (FMD) 7 hours compared to			
Secondary	To determine the effect active breaks compared to 7 hours of uninterrupted sitting on markers of glycaemia as assessed by continuous glucose monitoring (CGM). Glucose data gathered from closed-loop systems will be split into three time blocks; 1). 48 hours prior to the experimental period; 2). Experimental period (~7 hours); 3). 48 hours post-experimental period.	i) mean glucose j) % of time in level 2 hypoglycaemia (<3.0mmol/L) k) % of time in level 1 hypoglycaemia (3.0-3.9mmol/L) l) % of time in level 1 hyperglycaemia (10.0-13.9mmol/L) m) % of time in level 2 hyperglycaemia (>13.9mmol/L) n) glycaemic variability, reported as CV and SD o) episodes of hypoglycaemia and hyperglycaemia p) area under the curve of episodes of hypoglycaemia and hyperglycaemia.			
	To determine the effect of active breaks on insulin dose compared to 7 hours compared to uninterrupted sitting.	Closed-loop insulin delivery system			
	To determine the effect of active breaks on cerebrovascular function compared to 7 hours of uninterrupted sitting.	Middle cerebral artery velocity (MCAv)			
	To determine the effect of active breaks on markers of inflammation compared to 7 hours of uninterrupted sitting	5) Endothelin-1 (ET-1) concentrations 6) Vascular cellular adhesion molecule concentrations (VCAM-1) 7) Intracellular adhesion molecule (ICAM-1)			

### 5. Design and methods of data collection and data analysis

**Study design:** The study will use a randomised, crossover design, in which the same participants will complete two 7-hour experimental trials. One condition will involve participants sitting uninterrupted for 7-hours (*Sedentary*), while the other condition will require participants to interrupt 7-hours of sitting with 3-minutes of light-intensity walking every 30 minutes (*Active Breaks*). During both conditions, blood flow (peripheral and cerebral), arterial diameter and blood markers will be measured on two separate occasions (baseline and post (7hrs)). Interstitial glucose levels and insulin administrated by the hybrid closed loop will be recorded 7 days prior to, during and 7 days following each trial visit. Diet and physical activity for each participant will be controlled for 24-hours prior to and during and for the evening following each visit each trial visit.

The study will use a randomised, counterbalanced, crossover design, whereby participants will complete two experimental periods, each period will include a laboratory visit where the effects of 7 hours exposure to one of either 2 conditions will be investigated:

- A. Continuous sitting (Sedentary)
- B. 3 minutes of light-intensity walking every 30 minutes (Active Breaks)

Lab visits will be identical except for the condition and will be separated by at least 4 days. Females will be tested in the early follicular phase of the menstrual cycle to control for hormonal fluctuations. Female participants will be provided with the option to opt-out of a question relating to the menstrual cycle during the questionnaire and are welcome to talk to a female member of the research team on request. If they do not wish to disclose this information, then they will be excluded from the study and will not complete any further procedures.

#### **Pre-experimental procedures**

Potential participants will be sent a participant information sheet (PIS) via email. If, after reading the information sheet, they still wish to participate, they will attend a short online video call to discuss the study in more detail. During this video call the participant will have the opportunity to ask any questions about the study and eligibility will be assessed by the research team. Participants will then be asked to electronically sign an informed consent form (Dropbox Sign) in their own time. Should informed consent be gained, participants will complete a study-specific online questionnaire (via MS Forms), asking for data on age, sex, ethnicity, height, weight, medical history (including pregnancy), most recent HbA1c and diabetes history (duration of diabetes, hypoglycaemic events within the past 3 months).

#### Randomisation and Blinding

The order of condition will be randomised to either the *Sedentary* or *Active Breaks* conditions using a computer-generated random allocation sequence. Due to the nature of the study, blinding of the participants or researchers is not possible, however, participants and researchers will be blinded to experimental condition order (by keeping the order in a sealed envelope) until the morning of the first experimental visit.

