#### **Lab Visits**

Participants will be asked to avoid cycling or walking to the appointment on the mornings of each trial. They will be encouraged to use motor or public transport, arriving at the laboratory for ~07:30. Upon arriving at the laboratory, participants will be asked to complete a set of validated (Groningen Sleep Scale, International Physical Activity Questionnaire (IPAQ), Hospital Anxiety Depression Scale (IPAQ), SF-12 Health Survey, Diabetes Quality of Life (DQOL)), and non-validated questionnaires (perceived stress) on a computer before laying supine, starting a 60-minute 'steady state' period. This should take approximately 15 minutes. During the following 60 minutes resting blood pressure will be taken using an automatic device, and a superficial femoral artery (SFA) flow mediated dilation (FMD) ultrasound scan will be conducted using the non-invasive procedures described below. A transcranial doppler (TCD) ultrasound will assess cerebral blood velocity (CBv) and a Duplex ultrasound will measure the blood velocity and diameter of the internal carotid artery (ICA). Using a venepuncture, whole blood (3ml) will be sampled from an antecubital vein for the later analysis of baseline endothelin-1 (ET-1) Vascular cellular adhesion molecule (VCAM-1), Intracellular adhesion molecule (ICAM-1) and Interleukin-6 (IL6) concentrations. Blood will be drawn by a trained phlebotomist, and samples stored at -80° until later analysis using the procedures described below. Once this is complete (~09:00), participants will then be supervised while they sit at a workstation in an upright chair, minimising lower body movement.

During this time, food intake will be restricted until lunch (3.5 hrs). However, in the case of a hypoglycaemic episode (blood glucose <4mmol.l), participants will be provided with 15g of carbohydrates (Skittles). Blood glucose will be reassessed after 10-minutes. Should blood glucose still be <4.0 mmol/L, further 15 g of carbohydrates will be provided. The process will be repeated until blood glucose returns above 4 mmol.l.

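### The protocol rules out blinding for every researcher, provides no condition-masked reading of the primary FMD, and does not require the order envelope to stay sealed until the visit 1 baseline is done

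*Protocol*

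**What the plan says.** Section 5, Randomisation and Blinding, states that "blinding of the participants or researchers is not possible, however, participants and researchers will be blinded to experimental condition order", with no distinction between roles. The only protection offered is that the order of conditions stays in a sealed envelope "until the morning of the first experimental visit".

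The primary objective in section 4.2 reads "To determine the effect of active breaks on change in superficial femoral artery flow-mediated dilation (FMD"), compared with uninterrupted sitting. Section 5 adds that blood flow, arterial diameter and blood markers "will be measured on two separate occasions (baseline and post (7hrs")) in each condition, and that "the same participants will complete two 7-hour experimental trials".

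Under Lab Visits, participants arrive at about 07:30. In the hour of supine rest "a superficial femoral artery (SFA) flow mediated dilation (FMD) ultrasound scan will be conducted", together with the cerebral and carotid ultrasound and the blood draw. This is complete at about 09:00, when sitting begins. The first walking bout comes 30 minutes after the participant is seated. The FMD scan and the blood analysis are both said to follow procedures given further on, but no such procedures appear in the document.

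**The concern.** The statement that researchers cannot be blinded holds for those who supervise sitting and walking. It does not hold for someone who measures a saved recording or runs an assay on a frozen sample. By applying it to all researchers, the protocol gives up a protection that it could have kept, and it does so for the primary outcome.

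The hypothesis in section 2 is directional: breaks are expected to improve vascular function. The outcome is a change score, so knowledge of the condition can enter at the baseline scan as well as at the 7-hour scan. FMD measurement involves some reader judgement. That is general knowledge of the method, not a statement in the protocol. If readers know the condition, a systematic difference in reading goes straight into the treatment contrast, and a crossover analysis cannot remove it because it moves with the condition.

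**Working it through.** The plan gives no figure on this point, so the check is mainly a comparison of the protocol's own statements.

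**1. When is the condition needed, and until when is it concealed?**
- Arrival: about 07:30 (Lab Visits).
- Baseline measures complete and sitting starts: about 09:00 (Lab Visits).
- First walk: 09:00 + 30 minutes = about 09:30. Until then both conditions consist of sitting.
- Concealment promised: until the morning of visit 1, with no clock time and no position relative to the baseline scan.

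Opening at 07:30 and opening at 09:00 both satisfy the text. Nothing in the conduct of the visit requires the condition before about 09:30.

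**2. Who needs to know the condition?**
- Participants and supervising staff: yes.
- Readers of scans: no reason is given.
- Staff assaying blood: no. Samples are stored at -80° for later analysis (Lab Visits).

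**3. Does anything else in the protocol mask the reader?**
- Section 6: data are collected by a member of the research team.
- Section 8: vials carry a sample and a participant ID, which the investigative team can identify.
- Section 10.6: files are pseudonymised at collection, which hides the person. It is not described as hiding condition, visit or time point.

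No masked sonographer, coded recording or masked reader is mentioned anywhere.

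**4. How far does each remedy reach?**
- FMD scans planned: 24 participants × 2 conditions × 2 time points = 96.
- Late opening of the envelope covers the visit 1 baseline: 24 × 1 = 24 scans. With two conditions, knowing the visit 1 condition reveals that of visit 2, so the other 96 − 24 = 72 scans are outside its reach.
- Coded reading covers the measurement, though not the acquisition, of all 96.

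**5. Illustration of sensitivity, under assumptions only.** Section 7.2.1 gives n = 24 without alpha, power, effect size or SD. Assume a paired t-test with two-sided alpha 0.05, all 24 analysed and no true effect. Let b be a systematic reading difference between conditions, in SDs of the paired differences. The test statistic then has a noncentral t distribution with 23 degrees of freedom and noncentrality b × √24, where √24 = 4.899.

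| b (SD) | b × √24 | False-positive rate |
|---|---|---|
| 0 | 0 | 5% |
| 0.1 | 0.49 | 7.6% |
| 0.2 | 0.98 | 15.6% |
| 0.3 | 1.47 | 29.1% |
| 0.5 | 2.45 | 65.0% |

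For scale, the same test has 80% power at a true difference of 0.60 SD. The table shows how the test responds to a bias; it does not estimate one.

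**The case against.** **The envelope may well be opened after baseline.** A reader might infer that the protocol opens the envelope before the baseline scans. It does not say so. Opening at 09:00 on the day fits the wording exactly. This objection stands in full: the text is loose, and the defect is that it fails to exclude early opening.

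**The go/no-go decision.** A reader might also infer that early knowledge of the condition could sway whether a visit goes ahead on glucose grounds. The documents do not support this. Under Experimental Period the triggers are numeric, and a visit that fails them is rearranged, not dropped. No route to a biased contrast can be shown.

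**Sizing the bias from arterial diameter.** It is tempting to say that one FMD point is 0.06 mm of an assumed 6 mm artery, so that a shift of that size moves the result by a full point. That sizes no bias. With an assumed resting 6.00 mm and peak 6.30 mm, FMD is 0.30/6.00 = 5.00%. Shift both readings by 0.06 mm and it is 0.30/6.06 = 4.95%. A full point requires the peak alone to be misread, and an equal error at baseline and 7 hours cancels in the change score.

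**The reading method is unknown.** Because the promised FMD procedure does not appear, the document does not show that reading rests on unmasked judgement. That is fair. But the one stated rule declares blinding impossible for researchers as a group, and nothing in the document offsets it.

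**It might be left to the SAP.** Who is blinded, and until when, is a matter of trial conduct, and the protocol itself fixes it here.

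**Blood samples are partly covered.** The stated vial label carries no condition. That reduces the concern for the assays, but the team can still identify the samples.

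**Conclusion.** The point holds in a limited form. The protocol declares blinding impossible for all researchers, where that is true only for participants and the staff running the visit. It provides no condition-masked reading of the primary FMD. It guarantees concealment of the order only up to a morning on which the visit 1 baseline is also measured, without requiring the envelope to stay sealed until that baseline is complete.

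The size of any bias cannot be derived from the documents, and none is claimed. That part of the exposure is avoidable rests on two things: the protocol's own timeline, and the general premise that ultrasound recordings can be saved and read later. For blood, the protocol's own storage plan shows that coded assay is possible. This is a change that should be made; it is not evidence that the trial's result will be biased.

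**What to change.** Three changes to section 5, Randomisation and Blinding:

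1. Restrict the statement that blinding is not possible to participants and the staff running the visit.
2. State that the envelope is opened only once all visit 1 baseline measures are complete, at about 09:00. This protects the visit 1 baseline only.
3. Save the ultrasound and transcranial Doppler recordings, and label blood tubes, under codes that hide condition, visit and time point. Have existing team members read or assay them against the codes, and lock the results before the code is broken.

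The second change costs nothing. The third costs file-coding work, with no extra reader, scan, visit or participant. If the three sites read each other's coded files, this must be squared with section 10.9, which limits the full dataset to the Birmingham group unless a formal request is approved. Bias from acquisition by a sonographer who knows the condition remains and should be acknowledged as a limitation.

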#### Physical activity monitoring, interstitial glucose, insulin and carbohydrate intake

Participants will be provided with an activPAL physical activity monitor to wear for 48 hours prior to the first trial and will be requested to wear a second monitor between trials in order to standardise physical activity. Participants will also be provided with an online diary (MyFitnessPal) to record their diet for 48 hours prior to each trial and for 48 hours following each trial. A member of the research team will set up the MyFitnessPal account. To do this an email address, password, name, date of birth and sex will be entered into the app. The research team will set up a unique user profile for this service. These will be created using no personal details, with study codes used for all personal data entries. Glucose and insulin will be continuously recorded using the closed-loop system. Interstitial glucose will be continuously measured throughout the study period, with participants continuing to use their own continuous glucose monitor for the duration of the study. To access data, the research team will ask participants to share their glucose reports from their device's data management platform (e.g. LibreView for Abbott devices or Dexcom Clarity for Dexcom devices) for 4 weeks prior to the study and for 4 weeks following the study. This will be to ensure behaviour changes that have affected glucose levels have not occurred as a result of enrolling into the study. Once the participant has finished both trials and all research data have been downloaded after 4 weeks, the research team will cease using the glucose and insulin remote data-sharing link.

#### Standardisation of diet

Participants will be provided with a food diary for 48 hours prior to each lab visit. In addition, two mixed-macronutrient meals (dinner and breakfast) will be provided for participants to consume at home on the evening prior to (between 17:00-20:00) and on the morning of each lab visit (between 06:00-07:00). These meals will be home delivered, using a food delivery service on the days leading up to each lab visit. A third mixed-macronutrient meal will be provided for participants to consume on the day of each lab visit. All food will be pre-packaged and commercially available, with detailed instructions will be given to each participant for when they should consume each item. All meals will aim to provide 33.3% of estimated energy requirements based on body mass, with a target macronutrient profile of 12-15% energy from protein, 30-33% energy from fat, and 53-55% energy from carbohydrate. They will be asked to avoid further food intake other than when it is necessary to prevent or treat a hypoglycaemic event (glucose readings <4mmol.l).

#### **Experimental Period**

On the morning of each lab visit, participants will be contacted to confirm that they have consumed their standardised meals and that their glucose levels are within the range of 4-10 mmol.l. Prior hypoglycaemia has the potential to affect subsequent vascular function measures (Pena et al., 2012). As such, experimental visits will be re-arranged if blood glucose concentrations are not within this range or if participants have experienced one or more sustained (>90 minutes) hyperglycaemic (glucose readings >10mmol.l) or sustained (>30 minutes) hypoglycaemic episodes during the previous 24-hours.

